6.2 Participant Exclusion Criteria

A patient who meets any of the following criteria will be excluded from participation in this study:

- Does not own a smart phone with internet access
- Unwilling or unable to provide informed consent
- Myocardial infarction or stroke in the past 3 months
- Pregnant or breastfeeding
- Use of tobacco cessation medication in the past week
- Previously enrolled in the study

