9.1.2 Baseline survey (day 0; in dental practice)

The baseline survey will be administered prior to the intervention. It includes the following measures:

- Contact information
- Demographics (biological sex, gender, ethnicity, race, age)
- Toothbrushing habits
- Smoking history (cigarettes per day, time to first cigarette in the morning, previous quit attempts, past cessation treatment)
- Interest in quitting
- Confidence to quit
- Attitudes about nicotine replacement therapy

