12.2 Sample Size Considerations

The primary outcome for the UH3 trial is biologically verified (via CO testing) 7-day point prevalence abstinence (PPA) from use of combusted tobacco at 6-months post-intervention, and the power calculations presented here pertain to this outcome only.

Calculations were done using a variety of assumptions for cluster size (the number of patients per cluster, which we assumed was fixed across clusters), the Intraclass Correlation Coefficient (ICC), the PPA in the ET group ($P_{\neg ET}$), and the PPA in the NRTS group ($P_{\neg NRTS}$). Specifically, we used ICCs of .01, .013, and .016; cluster sizes of 20, 22, and 24 (corresponding to total sample sizes 1000, 1100, and 1200); $P_{\neg ET}$ values of 4.5%, 5%, and 5.5%; and effect sizes ($P_{NRTS} - P_{ET}$) of 5%-7% in increments of 0.5%. The number of clusters was kept fixed at 50, and all calculations assumed a type 1 error of 5% and a two-sided test.

For the ICC, we observed a value of .013 in preliminary studies and assume that is the most likely ICC we will observe in our study. The P-ET range was based on the observed value of 4.7% in preliminary studies and further assumes CO will verify only 85% of self-report. We believe the effect size range represents achievable intervention effects, and brackets the effect size of 5.5% seen in a similar study.

The target cluster size of 24 was chosen to provide approximately 80% power to detect effect sizes of 5.0 percentage points or greater assuming an ICC of 0.013 and a rate in the ET arm of 5.5% (Table 11.1). Using the point estimates of 4.7% for ET and the effect size of 5.5% seen in a similar study would result in almost 90% power. With an ET rate of 5.5%, power increases to over 90% for effect sizes of 6 percentage points or more, and over 94% for effect sizes of 6.5 percentage points or larger.

Table 11.1. Power to detect given effect sizes

ICC	# clusters	cluster size	Total N	Power					
				Prob in ET arm	Diff in quit rate between NRTS and ET arms				
				5.0%	5.5%	6.0%	6.5%	7.0%	
0.010	50	24	1200	4.5%	86.8%	91.5%	94.7%	96.9%	98.2%
				5.0%	84.6%	89.8%	93.5%	96.0%	97.7%
				5.5%	82.4%	88.1%	92.2%	95.1%	97.1%
0.013	50	24	1200	4.5%	84.9%	90.0%	93.6%	96.1%	97.7%
				5.0%	82.6%	88.2%	92.2%	95.1%	97.0%
				5.5%	80.3%	86.3%	90.8%	94.1%	96.3%
0.016	50	24	1200	4.5%	83.0%	88.5%	92.4%	95.2%	97.1%
				5.0%	80.6%	86.5%	90.9%	94.1%	96.3%
				5.5%	78.3%	84.5%	89.3%	92.9%	95.4%

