12.3 Final Analysis Plan

Demographics, baseline smoking history, and smoking behavior will be summarized across the aggregate sample and descriptively compared between clinics and treatment groups. Any large imbalances at the individual level will be considered for inclusion as a covariate. We will include the cluster-level stratification factors as covariates (minority race/ethnicity and payer mix). The distribution of each of the primary and secondary

study outcomes will be assessed using both parametric and graphical methods to determine the most appropriate modeling distribution (e.g., binomial, normal and zero-inflated distributions). Transformations of the outcome (e.g., log transform towards normality) will be considered if a model does not meet its assumptions. We will report point estimates (unstandardized effects size/magnitude) and associated 95% confidence intervals (precision). All hypotheses will be evaluated at a two-tailed alpha level of .05.

Sex and race as biological variables. We will test for effect modification by sex and race for the primary outcome. However, insofar as our proposal does not include hypotheses regarding sex and racial differences in treatment outcomes, we will conduct our hypothesis testing using both sexes and all races combined. This will be accomplished by adding a product term of group and sex or race (each will be evaluated separately) to the model. Given the low power for interaction effects, we will report the simple effects and associated confidence intervals both numerically and graphically to determine the nature of any effect modification.

[figure not shown]

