We will test whether NRT utilization, perceptions of NRT effectiveness and safety, intent to use NRT, and intent to quit mediate the relationship between study group (ET vs NRTS) and smoking abstinence using a cross-lagged panel model (CLPM) in a structural equation modeling (SEM) framework.^{48,49} In a CLPM, the mediator and outcome at time t is regressed on arm, the mediator at $t-1$ and the outcome at $t-1$. Prior to estimating a final model, we will test for stationarity for the structural paths by comparing whether a model in which the paths are invariant fits significantly worse than one in which the paths are free to vary. We will also include the same set of covariates used in the primary analysis as time invariant covariates We will assess model fit using root mean square error of approximation (RMSEA) and the comparative fit index (CFI). Our criteria for good model fit will include an RMSEA of .08 or below⁵⁰ and a CFI of .95 or above.⁵¹ A significant indirect effect,⁵² based on bootstrapped standard errors,⁵³ would provide evidence for mediation.^{48,54} We will account for the clustering of participants within practices by including a random effect for the intercept terms in each path equation by employing the multilevel form of SEM (2-1-1-1 design).^{55,56} We will conduct separate models for each mediator.

Figure X. Cross lagged panel model for testing mediation. Covariates omitted for clarity.

Missing data. For all participants, we will attempt to gather follow-up information and reasons for dropout regardless of protocol completion and censor at the point of drop out. PBRN studies routinely attempt to collect reasons for dropout.⁵⁷ We anticipate

having about 11% attrition, as was found in previous work. We will compare baseline data between those with and without missing data and examine whether there are variables that are related to missingness. Analysis will use maximum likelihood (ML) approaches to produce estimates of the model parameters. One advantage of a ML approach when compared to other approaches such as multiple imputation, is that it makes use of all available data without requiring imputation of missing values, it is more efficient, and maintains congeniality between the missing data estimation and the analytical model.⁵⁸ ML estimates have been shown to be consistent when missing data is related only to covariates and observed values of the outcome.^{59,60}

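### For Hypothesis 3a, the mediation covariates are chosen by arm imbalance, which does not protect the self-selected path from NRT use to abstinence against confounding by motivation to quit

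*Protocol*

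**What the plan says.** Section 12.3 of the protocol tests mediation with a cross-lagged panel model. Mediator and abstinence at each wave are regressed on arm and on both variables at the preceding wave. One model is fitted per mediator. On covariates it says: "We will also include the same set of covariates used in the primary analysis as time invariant covariates".

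The same section describes the primary-analysis set. The stratification factors (practice-level minority share and payer mix) are always in. For patient-level variables the rule is: "Any large imbalances at the individual level will be considered for inclusion as a covariate". The paragraph on the primary model also mentions adjustment for patient and practice factors, without naming any.

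A significant indirect effect, tested with bootstrapped standard errors, is taken as support for mediation. The general rule applies: "All hypotheses will be evaluated at a two-tailed alpha level of .05". The section states no assumption about confounding of mediator and outcome, and it plans no sensitivity analysis for it.

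The baseline survey (section 9.1.2) collects "Interest in quitting", confidence to quit, cigarettes per day, time to first cigarette, previous quit attempts and past cessation treatment.

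**The concern.** The indirect effect in Hypothesis 3a is the product of two paths, arm to NRT use and NRT use to abstinence. Only one arm is handed NRT, so the first path is almost certain to be non-zero. The decision therefore rests on the second path.

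That path is not randomised. Section 7.4 leaves it to the participant whether to use either product, both or neither. A patient keen to quit is more likely to open the samples and also more likely to stop smoking. Arm imbalance is a reasonable screen for a comparison between arms, but it says nothing about this path, because a common cause of use and quitting biases it even when the arms are identical at baseline. Randomisation tends to balance motivation, so the rule will normally leave it out.

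The lagged terms help little at the first wave. One exclusion criterion in section 6.2 is "Use of tobacco cessation medication in the past week", and section 6.1 requires near-daily smoking, so recent NRT use and abstinence are nearly constant at baseline. With one model per mediator, quit intention does not enter the NRT-use model either.

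At stake is the trial's claim about mechanism. A positive result for 3a could not distinguish an effect of NRT use from motivated smokers both using the samples and quitting.

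**Working it through.** **Inputs from the protocol.** Section 12.2: "The number of clusters was kept fixed at 50" and "The target cluster size of 24 was chosen to provide approximately 80% power to detect effect sizes of 5.0 percentage points or greater", at ICC 0.013 and an ET rate of 5.5%. Also "all calculations assumed a type 1 error of 5% and a two-sided test".

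**The plan's own figure first.** The protocol gives no operating characteristic for the mediation test, so the check is on primary power.
- Effective n per arm = 600 / (1 + 23 × 0.013) = 600 / 1.299 = 461.9.
- Unpooled SE = √[(0.055 × 0.945 + 0.105 × 0.895) / 461.9] = √(0.14595 / 461.9) = 0.01778.
- Power = Φ(0.05 / 0.01778 − 1.960) = Φ(0.853) = 80.3%, as Table 11.1 states.

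The pooled formula gives 80.1%. Over all 45 cells of the table the unpooled formula is within 0.05 points. The design inputs are therefore read correctly.

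**Inputs that are assumptions.** The documents give no NRT-use rates and no strength for motivation. Two simulations were run, each with 50 practices of 24, practice ICC 0.013 or about that, abstinence of about 5-9%, lagged abstinence in the model and no effect of NRT use on abstinence. Motivation was given the same odds ratio (OR) per SD on use and on quitting.
- Simulation A: use 10% vs 55%; arm → use at 1 month → abstinence at 3 months → abstinence at 6 months; no arm effect on abstinence; 600 trials per setting; 600 practice-level bootstrap draws; nominal error 5%.
- Simulation B: use 15% vs 60% at 1 month; use-to-abstinence path held equal over two lags; practice-clustered SEs; 400 trials per setting. Mediation was declared when the 95% Monte Carlo interval for the product lay above zero, so nominal error is 2.5%.

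**False mediation under the plan's adjustment**

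| OR per SD | A (nominal 5%) | B, no arm effect (nominal 2.5%) | B, direct arm effect of 5 points (nominal 2.5%) |
|---|---|---|---|
| 1.0 | not run | 2.8% | 3.7% |
| 1.25 | not run | 5.2% | 7.2% |
| 1.5 | 6% | 11.3% | 13.5% |
| 1.8 | 16% | not run | not run |
| 2.0 | 24% | 48.5% | 60.5% |
| 2.5 | 63% | 85.5% | 90.7% |

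At OR 1.0 the rate in B is close to nominal, so the excess comes from the confounding. The spurious use-to-abstinence OR in B averages 1.04-1.06 at 1.25, 1.15-1.16 at 1.5, 1.51 at 2.0 and 1.88-1.92 at 2.5.

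**After adding baseline motivation**
- Measured without error: 4-6% in A, 2-5% in B.
- Reliability 0.7 (A): 5%, 7%, 9% and 15% at OR 1.5, 1.8, 2.0 and 2.5.
- Reliability 0.5 (B, OR 2.0, direct arm effect): from 61% down to 19%.

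**The case against.** - **The covariate set is not fully closed.** Section 12.3 refers to unnamed patient and practice factors in the primary model, and an analysis plan that is not shown could list interest in quitting among them. It would then carry over to the mediation models. This stands in part. But the only selection rule that the protocol states for patient-level variables is arm imbalance, and the mediation models are tied to its result.
- **A reader might infer that all the mediation models ignore motivation and adjust for the primary covariates alone.** The text does not support that. Each model also conditions on arm, the lagged mediator and lagged abstinence. Section 4.2 measures quit intention, attitudes and intention to use NRT at baseline, so the quit-intention model carries its own baseline value and is less exposed. NRT use is listed there only at 1, 3 and 6 months. The point bears mainly on Hypothesis 3a.
- **The percentages are unstable.** This stands. At OR 2.0 the simulations give 24% and 49-61%. They differ in use rates, path structure and rejection rule, and neither refits the planned multilevel model. At OR 1.5, Simulation A shows 6% against 5%, which is no material inflation.
- **A reader might infer that the trial would report proof of mechanism, or that its main result is compromised.** Neither follows. The protocol calls a significant indirect effect evidence, not proof, and the primary comparison is between randomised arms.
- **More covariates strain a sparse model.** With 5-9% abstinent among 1200 there are about 60-108 abstainers per wave. This argues for a short covariate list, not for none.

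**Conclusion.** The point holds for Hypothesis 3a. Arm imbalance is the wrong criterion for choosing covariates on a path that participants select for themselves, and the decision rule states neither the assumption it needs nor a check on it. The direction is clear if motivation raises both use and quitting: the use-to-abstinence path is biased upwards and false mediation becomes more likely.

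The size is not known. Under assumed use of about 10-15% vs 55-60% and equal motivation odds ratios on use and quitting, false mediation is only slightly raised at OR 1.25, 6-14% at 1.5 and 24-61% at 2.0, against nominal 5% (A) or 2.5% (B). These figures are illustrations, not estimates for this trial. This is a worthwhile, inexpensive improvement to a secondary analysis.

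**What to change.** In the NRT-use mediation model, pre-specify a short set of baseline covariates in both the mediator and the outcome equations, regardless of arm balance: interest in quitting, confidence to quit, and one dependence measure (cigarettes per day or time to first cigarette). Use the same set in the other mediator models where the variable is not already present as the lagged mediator. Hold the coefficients equal over waves if the small number of abstainers makes estimation unstable.

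Add a sensitivity analysis for residual mediator-outcome confounding. State that a significant indirect effect is evidence for mediation only if no unmeasured mediator-outcome confounding remains.

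The cost is analysis wording; all these variables are in the baseline survey. Three covariates in two equations add 3 × 2 = 6 coefficients per model if held equal over waves, or 6 × 3 = 18 if left free over three follow-up waves. The limit is that motivation measured with error is only partly adjusted for, so bias is reduced but not removed. The sensitivity analysis is therefore needed as well.

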4 OBJECTIVES AND OUTCOME MEASURES

4.1 Primary

Objective	Brief Description/Justification of Outcome Measure	Outcome Measured By	Time Frame

Assess the effectiveness of NRTS compared to ET on 6-month biologically verified 7-day point prevalence abstinence from combusted tobacco
	
Seven day point prevalence abstinence (no combustible tobacco use in the past 7 days) is the recommended outcome for cessation induction trials as it measures a clinically-significant change in the long term, but reflects that participants may quit at any time following the intervention.⁴¹ Biochemical verification with breath carbon monoxide adds additional rigor to the primary outcome.⁴² Carbon monoxide will detect combustible tobacco use and not nicotine replacement therapy use.
	
Self-report survey using timeline follow-back and iCO quit personal CO monitor.
 
Following the CO test and result, we will compute a binary variable: abstinent vs. non-abstinent. Those who report abstinence on all 7 days prior to the 6-month follow-up and have a CO test result of <6ppm will be considered abstinent. Those who report smoking in the past 7 days, or have a CO result >6ppm, or who do not respond to the survey will be classified as non-abstinent.
	
6 months following baseline

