4.2 Secondary

Objective	Brief Description/ Justification of Outcome Measure	Outcome Measured By	Time Frame
Assess the effectiveness of NRTs compared to ET on 1-month self-report 7-day point prevalence abstinence from combusted tobacco	The Society for Nicotine and Tobacco Research recommends measuring outcomes of clinical trials at multiple timepoints to determine at what point interventions may be having an effect. ⁴¹	Self-report survey using timeline follow-back. From the timeline follow-back we will compute a binary variable with those who report no smoking on all 7 days prior to the assessment classified as abstinent, those who report smoking on any of the past 7 days classified as non-abstinent. Those missing smoking status data will be classified as non-abstinent.	1-month following baseline
Assess the effectiveness of NRTs compared to ET on 3-month self-report 7-day point prevalence abstinence from combusted tobacco	The Society for Nicotine and Tobacco Research recommends measuring outcomes of clinical trials at multiple timepoints to determine at what point interventions may be having an effect. ⁴¹	Self-report survey using timeline follow-back. From the timeline follow-back we will compute a binary variable with those who report no smoking on all 7 days prior to the assessment classified as abstinent, those who report smoking on any of the past 7 days classified as non-abstinent. Those missing smoking status data will be classified as non-abstinent.	3-months following baseline

Objective	Brief Description/ Justification of Outcome Measure	Outcome Measured By	Time Frame

Assess the effectiveness of NRTS compared to ET on 24 hour quit attempts.
	
24-hour intentional quit attempts reflect periods of abstinence due to an attempt to quit (not abstinence due to other reasons such as hospitalization etc.). FreSH is a cessation induction study. Thus, we measure the effect of NRTS to induce cessation behavior including quit attempts.
	
Self-report survey item from the Phenx toolkit. We will measure this item on the 1-, 3- and 6-month follow-up survey. We will then create a dichotomous variable indicating whether there has been a quit attempt at any time in the past 6 months by classifying any participant reporting a quit attempt on any follow-up survey as having had a quit attempt. Those who did not report a quit attempt on any survey will be classified as not having a quit attempt.
	
6 months following baseline

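### Protocol 4.1 counts survey non-responders as non-abstinent, 12.3 censors them with no outcome exempted, and a self-reported quitter without a CO result falls in neither class

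*Protocol*

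**What the plan says.** Protocol 4.1 defines a binary primary outcome.

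- Abstinent: participants who report no smoking on all 7 days and "have a CO test result of <6ppm will be considered abstinent".
- Non-abstinent: participants who admit to any smoking in that week, participants whose CO reading is above 6 ppm, and survey non-responders. For the last group the text reads "or who do not respond to the survey will be classified as non-abstinent".

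Protocol 4.2 has a catch-all for self-reported abstinence at 1 and 3 months: "Those missing smoking status data will be classified as non-abstinent".

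Protocol 12.3 tests hypothesis 1 with a mixed-effects logistic model of the 6-month outcome. Its missing-data paragraph says that the study will, for all participants, seek follow-up information and "reasons for dropout regardless of protocol completion and censor at the point of drop out". It expects about 11% attrition and continues: "Analysis will use maximum likelihood (ML) approaches to produce estimates of the model parameters". It prefers this approach because it uses all available data and needs no imputation. It does not say which outcomes it covers.

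Protocol 9.1.6 mails the CO monitor after the survey to those who report abstinence and plans 14 days of reminders. It does not say how a participant is classed if the test is never taken.

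**The concern.** The document gives two treatments of the same people. Under 4.1 a survey non-responder has an observed primary outcome (non-abstinent) and stays in the denominator. Under 12.3, read as written, the same person is censored and contributes no 6-month outcome. Two analysts could therefore report different denominators, rates and odds ratios for the primary endpoint.

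The CO gap adds to this. A participant who answers the survey, reports 7 days of abstinence and returns no test meets neither definition in 4.1. If that value were treated as missing under 12.3, only self-reported quitters could be removed in this way, so the exclusion would select on the outcome. The planning rates imply about 600 × 0.055 = 33 quitters in ET and 600 × 0.105 = 63 in NRTS, so a handful of classifications can matter.

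**Working it through.** **Inputs from Protocol 12.2, 12.3 and 6.4.1.** 25 practices per arm, 24 patients each; ICC 0.013; ET 5.5%, NRTS 10.5%; two-sided 5% test; 11% attrition; CO assumed to verify 85% of self-reports. Attrition by arm and the CO return rate are not in the protocol, so the values used below are assumptions.

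**1. The plan's own figure.** Effective n per arm = 25m / [1 + (m − 1) × ICC]. With m = 24: 600 / 1.299 = 461.9. SE = √[(0.055 × 0.945 + 0.105 × 0.895) / 461.9] = 0.01778. Power = Φ(0.05 / 0.01778 − 1.96) = Φ(0.853) = 80.3%, as in Table 11.1. The table therefore uses all 1200 participants.

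**2. What ML does in the primary model.** The hypothesis 1 model has one binary response per person, at 6 months. Smoking status at 1 and 3 months is not in it. A person without that response adds nothing to the likelihood, so ML on available data is a complete-case analysis: 1200 × 0.89 = 1068. The paragraph's appeal to observed values of the outcome suits repeated measures such as cigarettes per day, but this model has no earlier outcome to draw on.

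**3. Equal 11% loss, taking 5.5% and 10.5% as rates among responders.**
- Coded non-abstinent (4.1): 0.055 × 0.89 = 4.90%; 0.105 × 0.89 = 9.35%; difference 4.45 points; OR 2.00. SE 0.01686, power Φ(0.680) = 75.2%.
- Dropped (12.3): rates unchanged, OR 2.02. With m = 24 × 0.89 = 21.36, effective n = 534 / 1.2647 = 422.2 and power Φ(0.729) = 76.7%.

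If 5.5% and 10.5% already count non-responders as smokers, the 4.1 rule gives the stated 80.3%. Dropping them gives rates of about 6.2% and 11.8% and power of about 81.8%.

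**4. Unequal loss, still 11% overall (assumed splits, responder-rate reading).**

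| Loss ET / NRTS | Coded rates | Difference | OR coded | OR dropped, if missing at random |
|---|---|---|---|---|
| 8% / 14% | 5.06% / 9.03% | 3.97 points | 1.86 | 2.02 |
| 14% / 8% | 4.73% / 9.66% | 4.93 points | 2.15 | 2.02 |

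Power under the coded rule is 65.7% and 83.0% respectively. The odds ratios compare arm-level rates; they are not practice-specific model estimates.

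**5. Missing CO tests (assumed return r, on top of the 85% verification; survey loss set aside).** Self-report rate s = p / 0.85, which is 6.47% in ET and 12.35% in NRTS. Coded non-abstinent rate = p × r. Dropped rate = p × r / [1 − s(1 − r)]. Unclassified people = 600 × s × (1 − r).

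| r | Unclassified ET / NRTS | Difference, coded | Difference, dropped |
|---|---|---|---|
| 60% | 16 / 30 | 3.0 points | 3.2 points |
| 70% | 12 / 22 | 3.5 points | 3.7 points |
| 90% | 4 / 7 | 4.5 points | 4.6 points |

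**The case against.** The strongest reply is that the specific rule governs the general one. Section 4.1 defines the primary variable, 12.3 models that variable, and the missing-data paragraph follows the longitudinal and mediation models, where its reasoning fits. A mixed logistic model is fitted by ML in any case, so the ML sentence alone contradicts nothing. Table 11.1 uses the full 1200, which agrees with 4.1. For CO, a result below the cut-off is a necessary condition for abstinence in a two-level variable, so non-abstinent is the natural reading of a missing test.

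This reconciliation is plausible, and the protocol nowhere says outright that non-responders are dropped from the primary analysis. But it has to be supplied by the reader. The instruction to "censor at the point of drop out" is stated for all participants, in the section that analyses hypothesis 1, with no outcome exempted. The catch-all in 4.2 shows that the wording needed for missing status was available, yet 4.1 lacks it.

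A reader might go further and infer that the planned power is wrong, or that the effect is badly eroded. The documents do not support that:
- 80.3% reproduces.
- The fall to about 75% depends on taking 5.5% and 10.5% as rates among responders, whereas 6.5.2 says the power calculations already account for 11% loss.
- The 8%/14% split is an assumption, and its mirror image raises the odds ratio.
- The 85% verification share may already include some non-return, so step 5 may count it twice.
- Accepting self-report from untested quitters would give a larger difference, but neither section allows that.

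Nor is the absence of a sensitivity analysis an error here, because that may sit in a statistical analysis plan.

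**Conclusion.** The concern holds as a conflict of stated rules, plus an incomplete definition, on the primary endpoint. As written, 12.3 applied to the primary model is a complete-case analysis of about 1068 people, while 4.1 requires all 1200.

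The numerical effect is small under equal 11% loss: 1.5 percentage points of power and 0.02 in the odds ratio. It grows only if loss differs by arm, in a direction that cannot be known in advance. For untested quitters, the choice between coding and dropping moves the difference by about 0.1 to 0.2 points over an assumed 60% to 90% return.

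The case for fixing it rests less on these sizes than on having one rule fixed before outcome data are examined, and on avoiding an exclusion that can remove only self-reported quitters.

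**What to change.** In 4.1, state that every enrolled participant is in the denominator, that abstinent requires both 7-day self-report and a CO result below the cut-off, and that everyone else, including anyone with no CO result, is non-abstinent. This also settles a reading of exactly 6 ppm, which now falls in neither class.

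In 12.3, state that the censoring and ML paragraph does not apply to abstinence in the hypothesis 1 and secondary abstinence models, and is limited to cigarettes per day and the mediation models. The mediation models must stay in its scope, because it is their only stated missing-data method.

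Reconcile 6.3 with 9.1.6 at the same time. Section 6.3 words the mailing of CO monitors for NRTS-arm abstainers only, while 9.1.6 covers all who report abstinence. If 6.3 were followed, no ET participant could be classed as abstinent.

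A sensitivity analysis, for example on self-reported abstinence, is optional and can go in the statistical analysis plan. The cost is a few sentences and a verified quit rate that may be slightly lower.
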